8.2.4 Serious Adverse Event Collection Time Frame

All SAEs (regardless of relationship to study) are collected from the time the subject signs the informed consent until the defined follow-up period stated in Section 7.1.5, and must be reported to the Shire Pharmacovigilance Department and Medical Monitor within 24 hours of the first awareness of the event until 30 days after the last dose of investigational product.

In addition, any SAE(s) considered “related” to the investigational product and discovered by the investigator at any interval after the study has completed must be reported to the Shire Pharmacovigilance Department within 24 hours of the first awareness of the event.

Note: Investigators will report all SAEs that occur \leq 30 days after the last dose of investigational product and related SAEs that occur $>$ 30 days after the last dose of investigational product to Shire Pharmacovigilance Department.

8.2.5 Serious Adverse Event Onset and Resolution Dates

The onset date of the SAE is defined as the date the event meets serious criteria. The resolution date is the date the event no longer meets serious criteria, the date the symptoms resolve, or the event is considered chronic. In the case of hospitalizations, the hospital admission and discharge dates are considered the onset and resolution dates, respectively.

In addition, any signs or symptoms experienced by the subject after signing the informed consent form, or leading up to the onset date of the SAE, or following the resolution date of the SAE, must be recorded as an AE, if appropriate.

8.2.6 Fatal Outcome

Any SAE that results in the subject’s death (ie, the SAE was noted as the primary cause of death) must have fatal checked as an outcome with the date of death recorded as the resolution date. For all other events ongoing at the time of death that did not contribute to the subject’s death, the outcome should be considered not resolved, without a resolution date recorded.

For any SAE that results in the subject’s death or any ongoing events at the time of death, the action taken with the investigational product should be recorded as “dose not changed” or “not applicable” (if the subject never received investigational product).

8.2.7 Regulatory Agency, Institutional Review Board, Ethics Committee, and Site Reporting

The sponsor and the clinical CRO are responsible for notifying the relevant regulatory authorities/US central Institutional Review Boards (IRBs)/EU central ethics committees (ECs) of related, unexpected SAEs.

In addition, the clinical CRO is responsible for notifying active sites of all related, unexpected SAEs occurring during all interventional studies across the SHP616 program.

The investigator is responsible for notifying the local IRB, local EC, or the relevant local regulatory authority of all SAEs that occur at his or her site as required.

9. DATA MANAGEMENT AND STATISTICAL METHODS

9.1 Data Collection

The investigators' authorized site personnel must enter the information required by the protocol on the CRF. A study monitor will visit each site in accordance with the monitoring plan and review the CRF data against the source data for completeness and accuracy. Discrepancies between source data and data entered on the CRF will be addressed by qualified site personnel. When a data discrepancy warrants correction, the correction will be made by authorized site personnel. Data collection procedures will be discussed with the site at the site initiation visit and/or at the investigator's meeting. Once a subject is randomized, it is expected that site personnel will complete the CRF entry within approximately 3 business days of the subject's visit.

9.2 Clinical Data Management

Data are to be entered into a clinical database as specified in the CRO's data management plan. Quality control and data validation procedures are applied to ensure the validity and accuracy of the clinical database.

Data are to be reviewed and checked for omissions, errors, and values requiring further clarification using computerized and manual procedures. Data queries requiring clarification are to be communicated to the site for resolution. Only authorized personnel will make corrections to the clinical database, and all corrections are documented in an auditable manner.

9.3 Data Handling Considerations

Data that may potentially unblind the treatment assignment (ie, investigational product serum concentrations, antibodies to investigational product, treatment allocation, and investigational product preparation/accountability data) will be handled with special care during the data cleaning and review process. These data will be handled in such a way that, prior to unblinding, any data that may unblind study team personnel will be presented as blinded information or otherwise will not be made available. If applicable, unblinded data may be made available to quality assurance representatives for the purposes of conducting independent drug audits.

9.4 Statistical Analysis Process

The study will be analyzed by the sponsor or its agent.

All statistical analyses will be performed using SAS® Version 9.1 or higher (SAS Institute, PPD [REDACTED]).

The statistical analysis plan (SAP) will provide the statistical methods and definitions for the analysis of the efficacy and safety data, as well as describe the approaches to be taken for summarizing other study information such as subject disposition, demographics and baseline characteristics, investigational product exposure, and prior and concomitant medications. The SAP will also include a description of how missing, unused, and spurious data will be addressed.

The SAP will be finalized prior to unblinding to preserve the integrity of the statistical analysis and study conclusions.

9.5 Planned Interim Analysis, Adaptive Design, and Data Monitoring Committee

There is no planned interim analysis, adaptive design, or data monitoring committee in this study.

9.6 Sample Size Calculation and Power Considerations

For the primary efficacy endpoint, the NNA, a sample of 44 subjects from the crossover sequences will provide approximately 90% power at an alpha level of 0.025 (1-sided) to detect a difference of 1.0 attacks per month between active treatment and placebo assuming a between-subject standard deviation of 2.0. This target is supported by the recently completed, dose-ranging, Phase 2 study with CINRYZE (0624-206).

Regarding the analysis of the key secondary endpoint, the proportion meeting criterion P_R relative to placebo, 44 subjects will provide >90% power to test the hypothesis H_0 : proportion ≤ 0.2 against H_1 : proportion > 0.2 , assuming the true proportion is 0.44 by using a 1-group Chi-square test at an alpha level of 0.025 (1-sided).

Previous communications have occurred between regulatory authorities and the sponsor regarding a Phase 3 study for the SC CINRYZE development program. The regulatory authority indicated that the Phase 3 study should be of sufficient size to have a 95% probability for detection of safety signals occurring with an incidence of 5% or greater of subjects.

With respect to safety, a Safety Analysis Set of 60 subjects ensures that if the true population event proportion of any subject with a particular event is at least 5%, then the probability of observing at least 1 such event in the Safety Analysis Set is >95%.

The sample size calculation was conducted using nQuery + nTerim 2.0.

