9.8 Efficacy Analyses

9.8.1 Primary Efficacy Endpoint

The primary efficacy endpoint is defined as the NNA during a treatment period. The NNA is expressed as the number of attacks per month (ie, 30.4 days) of exposure:

$$\text{NNA} = 30.4 \times (\text{number of attacks during treatment period}) / (\text{days of treatment period})$$

If a subject discontinues during the treatment period, the denominator of the NNA will be the days on treatment for that subject; this is equivalent to the last observation carried forward imputation method to impute the missing information following the subject's discontinuation.

The primary efficacy analysis will be conducted for the subjects in the Full Analysis Set (Section 9.7) that are randomized to Treatment Sequence 1 (A/B) or 2 (B/A) to evaluate of the efficacy of SC administration of C1 esterase inhibitor [human] liquid for injection compared to placebo. The null hypothesis to be tested is that the NNA of C1 esterase inhibitor [human] liquid for injection is greater than or equal to the NNA of placebo, and the alternative hypothesis is that the NNA of C1 esterase inhibitor [human] liquid for injection is less than the NNA of placebo as below:

$$H_0: \mu_{\text{C1 INH}} - \mu_{\text{placebo}} \geq 0 \text{ vs}$$

$$H_1: \mu_{\text{C1 INH}} - \mu_{\text{placebo}} < 0$$

The primary efficacy endpoint will be analyzed by using a linear mixed effect model with period, sequence, stratification factor (use of prophylactic therapy with C1 INH), and treatment as fixed effects, and subject nested within sequence as a random effect. The mean treatment difference ($\mu_{\text{C1 INH}} - \mu_{\text{placebo}}$) will be estimated with a 95% CI.

To assess any carryover effect, a sensitivity analysis will exclude from the evaluation of the NNA any attacks occurring within the first 2 weeks of Treatment Period 2 for both sequences when carryover is suspected to be maximal. Since carryover should occur only with the A/B treatment sequence, its effect (if present) will be to spread C1 esterase inhibitor [human]

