1. INTRODUCTION

This is the full analysis Statistical Analysis Plan (SAP) for Study SHP616-300. The SAP provides a technical and detailed elaboration of the statistical analyses of safety and efficacy data as described in the study protocol amendment 4.0 dated 08 February 2017. Specifications for tables, figures, and listings will be provided in a separate document.

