2.5 Determination of Sample Size

The enrollment goal for this study is to randomize at least 66 subjects to ensure 54 subjects complete both treatment periods (44 for the crossover sequences, 10 for the active/active sequence).

For the primary efficacy endpoint, the normalized number of angioedema attacks (NNA), a sample of 44 subjects will provide 90% power at an alpha level of 0.025 (1-sided) to detect a difference of 1.0 attacks per month between active treatment and placebo assuming a standard deviation of the difference of 2.0.

Regarding the analysis of the key secondary endpoint, the proportion meeting criterion P_R relative to placebo, 44 subjects will provide 90% power to test the hypothesis H_0 : proportion

Page 18

 \leq 0.2 against H₁: proportion >0.2, assuming the true proportion is 0.44 by using a 1-group Chi-square test at an alpha level of 0.025 (1-sided).

With respect to safety, a Safety Analysis Set of 60 subjects ensures that if the true population event proportion of any subject with a particular event is at least 5%, then the probability of observing at least 1 such event in the Safety Analysis Set is >95%.

The sample size calculation was conducted using nQuery + nTerim 2.0.

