16. CHANGES TO ANALYSES SPECIFIED IN PROTOCOL

Not applicable.

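### Does the different label on the SD of 2.0 in Protocol 9.6 and SAP 2.5 undermine the 90% power for the primary endpoint?

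*Protocol*

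**What the plan says.** Protocol 9.6 states that "a sample of 44 subjects from the crossover sequences will provide approximately 90% power" at a one-sided alpha of 0.025, "to detect a difference of 1.0 attacks per month between active treatment and placebo assuming a between-subject standard deviation of 2.0". It cites the Phase 2 dose-ranging study 0624-206 in support of this target.

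SAP 2.5 repeats the calculation with the same 44 subjects, one-sided alpha, difference of 1.0 and 90% power, and names the same software, but describes the variability input by "assuming a standard deviation of the difference of 2.0".

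The primary model in Protocol 9.8.1 has period, sequence, the stratification factor "and treatment as fixed effects, and subject nested within sequence as a random effect". It is fitted to the A/B and B/A sequences only.

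SAP section 1 says that it elaborates the analyses "as described in the study protocol amendment 4.0 dated 08 February 2017". SAP section 16, on changes to analyses specified in the protocol, reads "Not applicable".

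**The concern.** The SD is the only variability assumption behind the primary-endpoint power, and the two documents describe it in terms that are not generally interchangeable. In a two-period crossover the treatment effect is estimated from each subject's own difference between periods, so precision depends on the SD of that difference. A between-subject SD most often means the spread of attack rates across subjects within one period. The two are linked only through the correlation between a subject's two periods, and neither document states it.

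Read that way, the protocol's input does not lead to its own 90%. If the correlation were low, 44 subjects would fall well short. A reader might then suspect that the trial was sized on the wrong quantity, or that the SAP had changed a planning assumption without recording it.

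**Working it through.** **Inputs.** From Protocol 9.6 and SAP 2.5: n = 44 crossover subjects, difference 1.0 attacks per month, one-sided alpha 0.025, SD 2.0. The between-period correlation (rho) is not stated, so it is treated below as an assumption and varied.

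**Step 1: the stated figure, taking 2.0 as the SD of the difference.**

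- Standard error = 2.0/√44 = 0.3015.
- Noncentrality = 1.0/0.3015 = 3.317.
- Paired t-test, df = 43: power 90.00%.
- Crossover t-test with a period effect, df = 42: power 89.97%.
- Normal approximation: Φ(3.317 − 1.960) = Φ(1.357) = 91.3%.

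By the paired t-test n = 43 gives 89.3% and n = 45 gives 90.7%, so 44 is the smallest sample that reaches 90%. That is strong evidence that 2.0 entered the calculation as the SD of the difference.

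**Step 2: the other reading, with 2.0 as the spread across subjects in each period.**

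SD of difference = 2.0 × √(2(1 − rho)). At n = 44, df = 43:

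| Assumed rho | SD of difference | Power | n for 90% |
|---|---|---|---|
| 0 | 2.828 | 63.0% | 87 |
| 0.25 | 2.449 | 75.4% | 65 |
| 0.4 | 2.191 | 84.1% | 53 |
| 0.5 | 2.000 | 90.0% | 44 |
| 0.6 | 1.789 | 95.2% | 36 |
| 0.75 | 1.414 | 99.6% | 24 |

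Power is within two points of 90% only for rho of about 0.47 to 0.535. At rho = 0.5 the formula gives 2.0 × √1 = 2.0, so the two labels then describe the same number.

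**Step 3: other readings.**

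- As the within-subject residual SD, the SD of the difference is 2.0 × √2 = 2.828 and power is 63.0%.
- As a parallel-group SD with 22 per arm, power is 36.7%.
- As the random-subject variance component, 2.0 cancels from the within-subject contrast and power cannot be computed from it.

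None of these gives the stated 90%.

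**Step 4: a plausibility check from the cited Phase 2 study.** Protocol 1.2.1.2 reports a mean within-subject difference of −0.61 (95% CI −1.23 to 0.01) in 22 subjects. The half-width is (0.01 + 1.23)/2 = 0.62, and the t quantile on 21 df is 2.080. The implied SD of the difference is 0.62 × √22/2.080 = 1.40. That study compared two active doses, so it is indirect evidence for a placebo comparison, but it gives no sign that 2.0 was optimistic.

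**The case for a change.** The best case for a change is that a reader of the protocol alone cannot reproduce the 90% without guessing what the SD refers to, and a reader of both documents meets two definitions of one number. Anyone who later compares the observed variability with the planning value has to choose between a single-period SD and the SD of the difference. The correction would cost one phrase, and SAP section 16 records nothing.

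Part of this stands. The protocol's wording is ambiguous, and neither document explains the change of label. But ambiguity is all that is shown. In a paired design the SD of the difference is itself a spread across subjects, namely of their individual treatment differences. The protocol's phrase directly follows a statement of the active-minus-placebo difference, so this reading is natural and agrees with the SAP.

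The argument from section 16 does not stand. That section concerns changes to analyses, and the description of a planning SD is not an analysis. Its entry is therefore not wrong on this point.

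**Conclusion.** The labels differ, and only the SAP's gives 90.0% at 44 subjects without further interpretation. The protocol's label gives the same figure if it means the spread of individual differences, or a single-period SD with an unstated correlation of 0.5. This is a clerical inconsistency in a planning assumption. It is not an arithmetic error, and it does not show underpowering. The 63.0% to 99.6% range above shows how far one reading depends on an assumed correlation and should not be taken as an estimate of this trial's power.

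No change follows, because there is nothing to gain. The SAP already states the quantity that the crossover analysis needs, and the effect of rewording on sample size, power, alpha, analysis and decision rule is nil.

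The conclusion rests on one inference. The software inputs are not in the documents, so that 2.0 was entered as the SD of the difference is deduced from SAP 2.5 and from 44 being the smallest sample to reach 90%. The sponsor could confirm this and align the phrase if either document is reopened for another reason, but it does not justify reopening one.

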9.7 Study Population

The **Screened Set** will consist of all subjects who have signed an informed consent.

The **Enrolled Set** will consist of all subjects who have signed an informed consent and some study procedures have begun.

The **Randomized Set** will consist of all subjects in the Screened Set for whom a randomization number has been assigned.

The **Safety Set** will consist of all subjects who have taken at least 1 dose of investigational product.

The **Full Analysis Set** will consist of all subjects in the Safety Set who have at least 1 post-baseline (eg, randomization) primary efficacy assessment.

The **Per-protocol Set** will consist of all subjects in the Full Analysis Set who complete scheduled primary assessments for 6 study weeks and who do not have pre-defined protocol deviations that may affect the primary efficacy endpoint.

The **Completer Set** will consist of all subjects in the Full Analysis Set who have completed the final scheduled primary assessment for the study.

The **Pharmacokinetic and Pharmacodynamic Set** will consist of all subjects in the Safety Set for whom the primary PK and PD data are considered sufficient and interpretable.

9.8 Efficacy Analyses

9.8.1 Primary Efficacy Endpoint

The primary efficacy endpoint is defined as the NNA during a treatment period. The NNA is expressed as the number of attacks per month (ie, 30.4 days) of exposure:

$$\text{NNA} = 30.4 \times (\text{number of attacks during treatment period}) / (\text{days of treatment period})$$

If a subject discontinues during the treatment period, the denominator of the NNA will be the days on treatment for that subject; this is equivalent to the last observation carried forward imputation method to impute the missing information following the subject's discontinuation.

The primary efficacy analysis will be conducted for the subjects in the Full Analysis Set (Section 9.7) that are randomized to Treatment Sequence 1 (A/B) or 2 (B/A) to evaluate of the efficacy of SC administration of C1 esterase inhibitor [human] liquid for injection compared to placebo. The null hypothesis to be tested is that the NNA of C1 esterase inhibitor [human] liquid for injection is greater than or equal to the NNA of placebo, and the alternative hypothesis is that the NNA of C1 esterase inhibitor [human] liquid for injection is less than the NNA of placebo as below:

$$H_0: \mu_{\text{C1 INH}} - \mu_{\text{placebo}} \geq 0 \text{ vs}$$

$$H_1: \mu_{\text{C1 INH}} - \mu_{\text{placebo}} < 0$$

The primary efficacy endpoint will be analyzed by using a linear mixed effect model with period, sequence, stratification factor (use of prophylactic therapy with C1 INH), and treatment as fixed effects, and subject nested within sequence as a random effect. The mean treatment difference ($\mu_{\text{C1 INH}} - \mu_{\text{placebo}}$) will be estimated with a 95% CI.

To assess any carryover effect, a sensitivity analysis will exclude from the evaluation of the NNA any attacks occurring within the first 2 weeks of Treatment Period 2 for both sequences when carryover is suspected to be maximal. Since carryover should occur only with the A/B treatment sequence, its effect (if present) will be to spread C1 esterase inhibitor [human]

liquid for injection efficacy into the placebo treatment period, thereby diluting the efficacy of C1 INH and favoring the null hypothesis of the primary efficacy analysis; it is not anticipated that any placebo effect will similarly benefit C1 esterase inhibitor [human] liquid for injection within the B/A treatment sequence. The study is powered to demonstrate superior efficacy even in the presence of carryover effects. Additional sensitivity analyses may be developed and included in the SAP.

Adjustments for multiplicity: To control the overall type 1 error, the primary and key secondary endpoints will be tested at the 0.05 significance level in the pre-specified order of the primary endpoint, key secondary endpoint 1, key secondary endpoint 2, and key secondary endpoint 3. Once one hypothesis test is not significant, the significance of all subsequent tests will not be assessed. The determination of a successful study is based solely on the results of the primary endpoint analysis regardless of the results for the key secondary endpoints.

9.8.2 Secondary Efficacy Endpoints

9.8.2.1 Key Secondary Efficacy Endpoints

1. The proportion of subjects meeting the criterion of at least a 50% reduction in the NNA during the 2000 IU C1 esterase inhibitor [human] liquid for injection treatment period relative to the placebo period.
2. The NNA excluding the first 2 weeks of each treatment period.
3. The proportion of subjects meeting the criterion of at least a 50% reduction in the NNA for the 2000 IU C1 esterase inhibitor [human] liquid for injection treatment period relative to the placebo period excluding the first 2 weeks of each treatment period.

Key secondary efficacy endpoints 1 and 3 are defined as achieving a $\geq 50\%$ reduction in the NNA (P_R) during the 2000 IU C1 esterase inhibitor [human] liquid for injection treatment period relative to the placebo period. Key secondary endpoints 1 and 3 will be analyzed as the proportion of subjects meeting criterion P_R . The null hypothesis is that P_R is less than or equal to 0.2, and the alternative hypothesis is that P_R is greater than 0.2. The proportion meeting criterion P_R will be estimated with an exact 95% CI. The lower limit of the 95% CI for the proportion will be compared with 0.2. This is equivalent to testing the null hypothesis against the alternative hypothesis at a 1-sided alpha level of 0.025 using the normal approximation to the binomial distribution.

Analysis of key secondary endpoint 2 will follow the same methods (ie, the linear mixed effect model) used for the primary efficacy endpoint.

9.8.2.2 Other Secondary Efficacy Endpoints

Other secondary efficacy endpoints to be evaluated in this study are:

- To determine the proportions of subjects achieving at least a 50% reduction in the NNA during a treatment period relative to the pretreatment assessment.
- Cumulative attack severity. This score is the sum of the maximum symptom severity recorded for each angioedema attack in a treatment period.

- Cumulative daily severity. This score is the sum of the severity scores recorded for every day of reported symptoms in a treatment period.
- Number of attack-free days during a treatment period.
- Number of angioedema attacks requiring acute treatment a treatment period.
- Disease activity as measured by the 98-day AAS. This score is the sum of the daily AAS during a treatment period, where the daily AAS is the sum of AAS items per day.
- Results of the AE-QoL questionnaire.
- Determine the response to icatibant when administered as treatment for an acute angioedema attack by:
 - Time to subject-assessed initial symptom improvement (TISI)
 - Time to subject-assessed complete symptom resolution (TCSR)

Subjects in the Full Analysis Set (Section 9.7) that are randomized to Treatment Sequence 1 (A/B) or 2 (B/A) will be used to assess the secondary efficacy endpoints in the evaluation of the efficacy of SC administration of C1 esterase inhibitor [human] liquid for injection compared to placebo. The treatment differences in clinical responder rate, both of which are defined within treatments, will be analyzed using McNemar's test for testing equality of proportions of responders within treatments. All other secondary endpoints will be analyzed using a linear mixed effect model with period, sequence, stratification factor (use of prophylactic therapy with C1 INH), and treatment as fixed effects, and subject nested within sequence as a random effect. The results of all secondary efficacy analyses will be summarized by the point estimate of within-subject treatment differences or response rates and the corresponding 95% CI. Descriptive statistics (n, median, 25% and 75% quartiles, and range) will be provided to summarize icatibant-related efficacy endpoints (TISI and TCSR) by treatment and icatibant-treated angioedema attack for all subjects in the Full Analysis Set. Where appropriate (for subjects ≥ 12 to < 18 years of age), other rescue medications used to treat acute angioedema attacks will also be summarized using descriptive statistics. In addition, angioedema attacks will be summarized by the maximum symptom severity and treatment for all subjects in the Full Analysis Set.

